- “Controlled Attenuation Parameter (CAP)” quantifies liver steatosis and is measured in dB/m (median of 10 subsequent valid measurements).

In addition quality control data are collected:

- Invalid measurements and success rate
- Number and list of valid measurements
- Inter quartile range (IQR) (kPa or dB/m) of all valid measurements within the examination (reflects the dispersion of stiffness or CAP measurements)
- IQR/med. (%) Indicates the IQR/median ratio and should remain as low as possible to ensure reliable results (goal < 30%)

Study withdrawal/discontinuation

The participant and/or participant’s family may withdraw from the study at any time. The study investigator can withdraw the participant from the study at any time if that is felt to be in the best interest of the participant and/or their family. If a participant in the longitudinal follow up study meets an endpoint for the end of the PUSH study (liver transplantation or death) they will have met the end of this study.

Statistical and Design Considerations

Based upon interest and involvement of the subjects in PUSH, we anticipate all subjects currently available (168) will enroll. If TE becomes available at the 3 centers without TE, then up to an additional 60 subjects would be available to enroll. TE would be available from all eligible US pattern subjects.

Hypothesis 1: TE results can differentiate children with a heterogeneous or homogeneous pattern on grayscale liver US who will progress to a nodular pattern on US

Analysis:

To test whether TE, when combined with US pattern characterization can improve the prediction of progression to a nodular pattern on US, we will build two discrete survival models using logistic regression. In the first model, greyscale US consensus grade will be used to predict prediction to nodular pattern. In the second model, we will add the predictor liver stiffness measured by TE. If the second model significantly increases the area under the receiver operating characteristic curve

August 12, 2016

(AUROC) comparing to the first model, we will conclude that TE can improve the prediction of progression to a nodular pattern on US. All subjects graded as NL, HMG, or HTG at the time this ancillary study starts will be included in the analysis.

Power calculations:

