The estimated 2-4 year progression rate is ~40% in HTG subjects. Thus of the 33 available with HTG pattern, 10-13 would be predicted to progress to CIR. However, as the study is in progress, ~20% have progressed so the risk of progression may be lower. We choose to make a conservative assumption in our power calculation: 20% of HTG subjects will progress to CIR pattern, and 2% of NL or HMG subjects will progress to CIR pattern. In addition, we assume the liver stiffness measure follow a lognormal distribution with location =0 and scale parameter =0.5 (i.e. median=1, Q1=0.71, Q2=1.4). With 142 subjects (approximately 63% NLs, 23% HTGs, and 13% HMGs) we will have 80% power to detect an odds ratio of 4 for a 1 unit increase in the liver stiffness measure. (Caveat: Given that we do not have any preliminary data of TE measures in CF subjects, the results of this power calculation only give us a general guidance).

Hypothesis 2a: Valid TE measurements will be obtained in more than 90% of children with CF

Analysis:

For hypothesis 2a, we will estimate the proportion of subjects in whom a valid transient elastography measurement can be obtained. At each site, all measurements will be performed by one of the trained examiners. The results will be reported as the median of 10 valid measurements and will be accepted as valid if the ratio of the interquartile range (IQR) and median was < 30% and the success rate was > 60% (8, 9). Per Goldschmidt 2013 (9) we will define two measures of the feasibility of transient in our population: “technically possible” and “acceptable quality.” The proportion of subjects with a “technically possible” FibroScan™ is defined as the number of subjects with at least 10 FibroScan™ measurements obtained divided by the number assessed. The proportion of subjects with FibroScans™ of “acceptable quality” is defined as the number of subjects with FibroScan™s with the ratio of the interquartile range and median of the 10 measurements <30%, divided by the number assessed. The proportions and their 95% confidence intervals will be provided using the Wald method. We will do a stratified (separate) analysis by <8 years of age and >8 years of age. There will be the opportunity to compare this data to children with other liver diseases in the ChiLDReN FORCE study.

Hypothesis 2b: To determine the variability of TE measurements taken at different liver sites in the same patient

Analysis

August 12, 2016

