For this analysis we will include all subjects with a nodular US pattern (CIR). The primary outcome will be a composite outcome defined as occurrence of any of the following three endpoints:

August 12, 2016

Hypersplenism: platelets <150,000
Variceal hemorrhage
Splenomegaly as indicated by a palpable spleen
Ascites as clinically detected ascites

A discrete survival analysis using logistic regression will be used to test whether transient elastography results are associated with risk of developing liver cirrhosis complications. The predictor will be most recent TE results.

Power calculation:

Previous literature has reported mean a rate of variceal hemorrhage between 5 and 10% per year with CF and cirrhosis. There is no data for rates of development of splenomegaly or thrombocytopenia in CF with a nodular US pattern. With currently 33 subjects with a nodular US pattern and 90% successful rate of TE, we anticipate 3 to 6 subjects (10% ~20%) among 30 subjects developing one of the endpoints in 2 years. We assume the true difference in population mean TE measurements is 19 kPa between subjects with and without portal hypertension; we assume the SD is 22.0 kPa and 6.0 kPa for subjects with and without portal hypertension, respectively. Our calculation shows that using 2-sided likelihood ratio Chi-square test (Type I error rate 5%) there will be 80% power to detect odds ratio 4 ~ 5 per 10kPa increase in TE results.

Hypothesis 6: TE assessment of liver stiffness and fat content will correlate with steatosis and fibrosis staging on liver biopsy in CF

Analysis: ANOVA or Kruscal-Wallis test, whichever is appropriate, will be used to compare TE measures between groups based on steatosis and fibrosis staging on liver biopsy in CF.

Human research participant issues

Institutional Review Board Approval

Local institutional review board approval will be obtained for the study. IRB approvals will be centrally collated at the Data Coordinating Center.

Standard of Care

Standards of care for the management of liver disease at each of the CFLD NET sites will be followed. At present there are no clinical standards for interventions based on TE-measured liver stiffness for pediatric CF patients and thus there are no expected interventions based solely on TE measurements.

Consent

Informed consent and assent (when appropriate according to local standards) will be obtained prior to any research activities. A common template for

August 12, 2016

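### The primary conclusion on Hypothesis 1 rests on a significant AUROC increase, but the stated 80% power is for the TE odds ratio and does not carry over to that rule

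*Protocol*

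**What the plan says.** Protocol, Statistical and Design Considerations, Hypothesis 1, Analysis: "we will build two discrete survival models using logistic regression". Model 1 uses the consensus ultrasound grade. For Model 2, "In the second model, we will add the predictor liver stiffness measured by TE". The decision rule follows: "If the second model significantly increases the area under the receiver operating characteristic curve" relative to Model 1, TE is concluded to improve prediction of a nodular pattern. No AUROC test and no significance level are named.

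Hypothesis 1, Power calculations: "With 142 subjects (approximately 63% NLs, 23% HTGs, and 13% HMGs) we will have 80% power to detect an odds ratio of 4" per unit of stiffness, assuming that "20% of HTG subjects will progress to CIR pattern, and 2% of NL or HMG subjects will progress to CIR pattern". The section gives no AUROC for either model, no target AUROC difference and no power for comparing the two. Its caveat, that the result is general guidance, is tied to having no prior TE data in CF.

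**The concern.** An odds ratio is the target of a coefficient test. A rise in AUROC is a different criterion, and when nested models are fitted and compared on the same few events it is usually a much less sensitive one. The protocol states both the rule and the power, and they do not belong together, so this is not a detail left to a later document.

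At stake is the primary question. A TE effect of exactly the planned size could be clear from the coefficient and still fail the rule, so the study would not conclude that TE helps. A reader of the protocol would believe the chance of missing it was 20%.

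**Working it through.** **Inputs from the protocol.** 90 NL, 19 HMG and 33 HTG subjects (total 142); progression of 20% in HTG and 2% in NL or HMG; stiffness X lognormal with log-scale mean 0 and SD 0.5 (median 1); "an odds ratio of 4 for a 1 unit increase in the liver stiffness measure". Expected events: 33 × 0.20 + 109 × 0.02 = 6.6 + 2.18 = 8.8.

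**Assumptions added.** Two-sided 5%, which is not stated for Hypothesis 1 but is stated for Hypothesis 5; the same stiffness distribution in every grade; one follow-up interval.

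**Model.** logit P = a(grade) + ln(4) × X, with ln(4) = 1.386. The 20% and 2% have two main readings:

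- Overall risks: a(grade) is solved so that P averaged over X equals 20% or 2%.
- Risks at median stiffness (X = 1): a(grade) = logit(risk) − 1.386. This gives −1.386 − 1.386 = −2.77 for HTG and −3.89 − 1.386 = −5.28 for NL and HMG, and 12.3 expected events.

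**Tests in each simulated trial.** Likelihood-ratio test (LRT): 2 × (logL of Model 2 − logL of Model 1) > 3.84. Paired DeLong test: (AUROC2 − AUROC1)/SE > 1.96. With 3,000 to 6,000 trials per setting, the simulation error is at most √(0.25/3000) = 0.9 points. Ranges cover grade coded in two or three levels and repeated runs.

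| Reading of 20%/2% | Events | LRT of TE | Paired DeLong |
|---|---|---|---|
| Overall risks | 8.8 | 70–73% | 37–39% |
| At mean stiffness | 10.8 | 78% | 41–44% |
| At median stiffness | 12.3 | 81% | 45–50% |
| Overall rate (6.2%) set at predictor means | 16.3 | 86% | 52–59% |

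**The protocol's own figure.** The 80% reproduces as power of the coefficient test with risks taken at median stiffness (81%). With overall risks the LRT has 70–73% two-sided, or 80% at one-sided 5%. A normal approximation (Hsieh) is a rough check: SD of X = √((e^0.25 − 1) × e^0.25) = 0.604; mean risk 8.78/142 = 0.0618; power = Φ(√(142 × 0.0618 × 0.9382) × 1.386 × 0.604 − 1.96) = Φ(0.44) = 67%.

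**Is DeLong merely conservative here?** No. With an odds ratio of 1, a significant increase occurs in 5–6% of trials, about the same as the LRT's 5–6%.

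**How often the two rules part.** In about 36% of simulated trials, under either main reading, the LRT is significant and the DeLong rule is not.

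**Sensitivity.**

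- 128 subjects (142 × 0.9, for 90% TE success), overall risks: LRT 68%, DeLong 35%.
- 40% progression in HTG: LRT 75%, DeLong 47%.
- One-sided 5%, overall risks: LRT 80%, DeLong 54–56%. The one-sided DeLong rule then rejects in 10–12% of trials when TE has no effect, so this is not a like-for-like gain.

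**Other AUROC tests (overall risks, small checks).**

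- Bootstrap with refitting: 54% in 500 runs (null rate 6.6%).
- Permutation of TE within HTG and non-HTG: about 57% in 500 runs (null rate 3.8%). The LRT had 73% in the same check.
- A separate refit-bootstrap check: 67% in 120 runs, standard error √(0.67 × 0.33/120) = 4.3 points.

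**The case against.** The strongest reply is that DeLong is not in the protocol. The choice of AUROC test may properly sit in an analysis plan that is not shown, and the gap narrows to about 16 points (73% against 57%) with a permutation test. That stands: the loss depends on the test. It does not rescue the 80%, which was calculated for none of these tests.

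The cohort is fixed by PUSH enrolment, so power did not set the sample size. The protocol calls its calculation general guidance and its 20% conservative. AUROC is also a natural measure when the objective is better prediction. All of this is fair and limits the consequence to a misattributed power and an insensitive rule. The caveat, however, concerns missing TE data and not the choice of test, and DeLong power stays below 50% even with 40% HTG progression. The simulation's single interval simplifies the planned discrete survival models.

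The wording "using 2-sided likelihood ratio Chi-square test" belongs to Hypothesis 5. It does not show which test was used for Hypothesis 1. That a coefficient test was powered follows from the target being an odds ratio.

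A reader might also infer two stronger points, and neither holds:

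- That a three-level grade makes the analysis inestimable. At 2%, the chance of no event is 0.98^19 = 0.68 in HMG and 0.98^90 = 0.16 in NL, so 1 − 0.32 × 0.84 = 0.73 that at least one is empty. But only that grade's coefficient diverges. The LRT of TE and the AUROC can still be computed, and power is much the same with two or three levels.
- That optimism corrupts the decision. With uninformative TE the apparent AUROC rises by 0.027 on average, and in 79% of data sets, but a significant rise at the two-sided 5% level occurs in only 5–6%. The optimism affects the reported size of the gain.

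**Conclusion.** The mismatch is real and lies in the protocol text: the primary rule is an AUROC increase, and the 80% is power for an odds ratio. If the rule is carried out with a paired DeLong test at two-sided 5%, power is about 37–39% where the coefficient test has 70–73%, and 45–50% where that test has the stated 80%. Across the four readings tabulated, the gap is 27 to 37 points. Resampling tests of the AUROC lie between, at roughly 54–67%, on few runs.

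It would be tempting to set 80% against 37%. No single two-sided calibration gives that pair: where DeLong has 37%, the coefficient test has a little over 70%. Nor do the documents show that DeLong will be used. These figures rest on the assumed test and level, one follow-up interval, and equal stiffness distributions across grades. That the stated power does not belong to the stated rule rests on none of these.

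**What to change.** In Hypothesis 1, Analysis, make the one-degree-of-freedom likelihood-ratio test of liver stiffness (Model 2 against Model 1) the decision rule, with its significance level stated. Report the AUROC change with an optimism-corrected bootstrap confidence interval as the measure of predictive gain. In Power calculations, name that test and say whether 20% and 2% are overall risks or risks at median stiffness, since the 80% depends on it.

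If the AUROC rule is kept, name its test and level and replace the 80% with the power of that test.

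Collapsing grade to HTG against NL or HMG is optional. The cost is wording only: same data, same two models, no added visits or subjects. It should be settled before outcome data are analysed.

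### As written, the Hypothesis 1 rule takes the AUROC gain from the same few-event data that fit the models and sets no direction for TE, so the reported gain is optimistic and a wrong-direction effect can count as success

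*Protocol*

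**What the plan says.** The Hypothesis 1 analysis states: "we will build two discrete survival models using logistic regression". The first uses the consensus ultrasound grade. For the other: "In the second model, we will add the predictor liver stiffness measured by TE". The decision rule begins "If the second model significantly increases the area under the receiver operating characteristic curve" and ends "AUROC) comparing to the first model, we will conclude that TE can improve the prediction of progression to a nodular pattern on US". The analysis set is stated as "All subjects graded as NL, HMG, or HTG at the time this ancillary study starts will be included in the analysis". No children are set aside, no resampling or other internal validation is mentioned, and no sign is required of the TE coefficient.

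The power paragraph that follows plans on "20% of HTG subjects will progress to CIR pattern, and 2% of NL or HMG subjects will progress to CIR pattern". It calls this conservative, having first noted "The estimated 2-4 year progression rate is ~40% in HTG subjects". It then states "With 142 subjects (approximately 63% NLs, 23% HTGs, and 13% HMGs) we will have 80% power to detect an odds ratio of 4" per unit of stiffness.

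Elsewhere the protocol describes liver stiffness as the measure that quantifies fibrosis. For the exploratory Hypothesis 4b it does fix a sign: only a significant negative coefficient for fat content supports that hypothesis.

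**The concern.** The first model has very few distinct predicted values if time terms are left aside, so many progressor/non-progressor pairs are tied. A continuous variable added to the model breaks those ties, and a coefficient estimated on the same children breaks them in whichever direction suits the sample. With so few events the apparent AUROC therefore tends to rise even when the variable carries no information.

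Two things are at stake. The first is the size of the gain, which is the number that answers the primary objective: it is biased upward, and proportionately most when TE adds little. The second is its meaning. The rule looks only at the AUROC, so a fitted model in which a stiffer liver predicts lower risk meets it as readily as one in which a stiffer liver predicts higher risk.

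**Working it through.** **Inputs (Hypothesis 1, Analysis and Power calculations).** 90 NL, 19 HMG and 33 HTG, so 142 children. Progression is 20% in HTG and 2% in NL or HMG. Stiffness is lognormal with location 0 and scale 0.5. The odds ratio is 4 per unit.

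**Assumptions not in the protocol.** Two-sided 5% level, DeLong test for the paired AUROCs, TE independent of grade, one record per child.

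**The plan's own figure.** The expected-information Wald formula for the TE coefficient, adjusted for HTG versus other and with the 20%/2% rates placed at the mean TE, gives 79.8% power. The stated 80% is thus reproduced, for the coefficient test.

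**Expected events.**
- Planning rates: 33 × 0.20 + 109 × 0.02 = 6.60 + 2.18 = 8.78.
- 40% HTG rate: 33 × 0.40 + 109 × 0.02 = 13.20 + 2.18 = 15.38.

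**Tied pairs under model 1 (three grades).** Expected progressors are 6.6 HTG, 1.8 NL and 0.38 HMG. Expected non-progressors are 26.4, 88.2 and 18.62, together 133.22.

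(6.6 × 26.4 + 1.8 × 88.2 + 0.38 × 18.62) / (8.78 × 133.22) = 340.1 / 1169.7 = 29%.

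**Simulation with no TE effect.** Both models were fitted and scored on the same 142 children, then scored on fresh data. About 4,000 studies were run per column for about 9 events and 2,500 for about 15.

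| | 9 events, HTG vs other | 9 events, three grades | 15 events, HTG vs other | 15 events, three grades |
|---|---|---|---|---|
| Mean apparent gain | +0.031 | +0.024 | +0.017 | +0.016 |
| Apparent gain above 0 | 80% | 80% | 78% | 81% |
| Mean gain in fresh data | -0.005 | -0.005 | -0.001 | -0.001 |
| Significant increase, two-sided 5% | 6.0% | 5.3% | 4.8% | 5.0% |
| of all studies: increase with negative TE coefficient | 2.8% | 2.6% | 2.3% | 2.6% |

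In the 9-event columns no study rejected downward. The share of false claims with a negative coefficient was 46% and 49% there; across all simulations run it was 40-49%.

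**True odds ratio 4, marginal 20%/2% rates.** Mean apparent gain was 0.099 (HTG vs other) and 0.085 (three grades), against 0.084 and 0.072 in fresh data. The excess is 0.015 and 0.013.

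**True odds ratio 1/4 (stiffer liver, lower risk).** The rule declared an improvement in 29-30% of studies, and in up to 38% in a separate run. All of these had a negative TE coefficient.

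**Effect of requiring a positive coefficient.** With no TE effect and about 9 events, false claims fall to 6.0 - 2.8 = 3.2% and 5.3 - 2.6 = 2.7%. If significance is judged instead by the likelihood-ratio test of the TE coefficient, the figures are 2.7% and 2.4%. At odds ratio 4 the requirement costs almost nothing: at most 0.13% of studies had a significant increase with a negative coefficient.

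**Effect of optimism correction.** In a smaller simulation (150 studies, 50 resamples, two-level grade, penalised fit), corrected against real gain was -0.004 against -0.004 with no effect, 0.027 against 0.028 at odds ratio 2, and 0.081 against 0.074 at odds ratio 4.

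**The case against.** The protocol never says that the AUROCs are apparent values. That is inferred from its silence, and a statistical analysis plan, not at hand here, could name the AUROC test and add internal validation. This stands as a limit on certainty. However, the protocol does fix the analysis set, the criterion and the conclusion, and as worded the claim can be made without any such step.

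Hypothesis 1 is also worded without direction: TE is to differentiate children who progress. A stable inverse association would genuinely help prediction; at odds ratio 1/4 the gain in fresh data was 0.041-0.051. This has force. Against it, the rationale is that stiffness measures fibrosis, and an inverse finding would need an explanation before it supported that rationale.

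The simulations simplify. A discrete survival model with period terms would have more than three predicted values, which would change the share of ties. About 9 events is the protocol's deliberately conservative case.

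A reader might also infer more than the documents support:
- **That the gain is always positive when TE is useless.** It is positive on average and in about 80% of studies.
- **That the false-claim rate is inflated.** The protocol decides on significance, and the two-sided 5% rate is about nominal. The 5-6% is both tails of the TE coefficient appearing as an AUROC increase.
- **That the larger gaps among significant results show this bias.** In one simulation at odds ratio 2, significant studies averaged 0.098 apparent, 0.093 corrected and 0.040 real. That is mostly selection on significance under low power, and optimism correction hardly touches it.

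**Conclusion.** The point holds in a limited form. Followed as written, the Hypothesis 1 rule gives an upward-biased estimate of what TE adds: by about 0.03 when TE adds nothing and about 9 events occur (0.024 to 0.031 apparent against -0.005), about 0.017 with 15 events, and about 0.013-0.015 at odds ratio 4. The overall false-claim rate is not the problem. What is wrong is that all false claims say TE improves prediction, and that close to half of them rest on an effect opposite to the fibrosis rationale.

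The figures rest on in-sample scoring as the plain reading, a two-sided 5% DeLong test, TE independent of grade and one record per child. This is worth correcting because it is cheap and touches the primary estimate. It does not invalidate the study and is not a must-fix.

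**What to change.** In the Hypothesis 1 analysis paragraph:

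1. Report the AUROC gain with bootstrap optimism correction as the primary estimate, beside the apparent value. Refit both models in every resample.
2. Conclude that TE improves prediction only if the planned test is significant and the TE coefficient is positive.

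A further condition that the corrected gain exceed zero is not needed. In simulation it held in every significant study, so it would change no decision.

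The cost is a change of wording and a few lines of code, with no new data. The reported gain will be about 0.01-0.03 smaller, and a true inverse association would no longer count as success on the primary aim. It could still be reported as a finding. The correction does not remove the exaggeration that comes from looking only at significant results, and in the small simulation it left 0.081 - 0.074 = 0.007 at odds ratio 4.
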